Short Title:	Switch to BIC/FTC/TAF after Renal Transplant
Clinical Phase:	IV
Principal Investigator:	[name]
Study Description:	Hypothesis: We hypothesize that BIC/F/TAF will be efficacious and safe in the management of HIV+ post renal transplant patients, and will have few adverse reactions and drug-drug interactions with tacrolimus in this population
Sample Size:	N = 20
Study Population:	Virally-suppressed HIV+ adults post-renal transplant
Enrollment Period:	November 2020 to May 2023
Study Design:	Single arm, open-label, switch study, following subjects for 48 weeks with a 6 month follow-up
Study Duration:	November 2020 – December 2024
Participant Duration:	In this single arm, open-label, switch study, we propose to switch virally suppressed HIV+ adults post-renal transplant to BIC/F/TAF and follow the subjects for 48 weeks with a 6 month follow-up (Section 6.1).
Study Agent:	BIC/F/TAF® (BIC/F/TAF)
Primary Objectives:	
 1. To determine the efficacy of BIC/F/TAF in HIV+ patients post renal transplant at 24 weeks and 48 weeks post-switch to BIC/F/TAF. 2. To assess the safety and tolerability of BIC/F/TAF in HIV+ patients post renal transplant at 24 weeks and 48 weeks post-switch to BIC/F/TAF. 3. To assess the pharmacokinetics of BIC/F/TAF in HIV+ patients post renal transplant and its interactions with immunosuppressive agents (Tacrolimus) at 12 weeks post-switch to BIC/F/TAF. 4. To assess renal biomarkers including urine protein/creatinine ratio; urine albumin/creatinine ratio; eGFR; serum BUN, creatinine and phosphorus; tacrolimus levels; retinol 2 binding protein and B2 microglobulin post renal transplant at 24 weeks and 48 weeks post-switch to BIC/F/TAF.
Secondary Objectives:	
 1. To assess the incidence of kidney graft rejection after switching to BIC/F/TAF post renal transplant at 24 weeks and 48 weeks post-switch to BIC/F/TAF. 2. To assess the immunologic activity (CD4 count/percentage) of BIC/F/TAF post renal transplant in conjunction with immunosuppressive agents (tacrolimus) at 24 weeks and 48 weeks post-switch to BIC/F/TAF. 3. To determine patient satisfaction with BIC/F/TAF post renal transplant by utilizing a questionnaire to assess health-related quality of life outcomes at 24 weeks and 48 weeks post-switch to BIC/F/TAF.

Primary Endpoints:

1. Proportion of subjects with plasma HIV-1 RNA <50 copies/ml at week 48.
2. Safety and tolerability (monitoring and recording adverse events) in subjects who switched from a prior ARV regimen to BIC/F/TAF.
3. Pharmacokinetics of BIC/F/TAF and tacrolimus, including intracellular TAF levels (dried blood spot, PBMC).

Secondary Endpoints:

1. Changes from baseline in CD4+ T lymphocyte cell count/percentages post renal transplant.
2. Incidence of rejection rates of the kidney transplant post renal transplant and correlation with tacrolimus levels.
3. Patient satisfaction with reduced pill burden and adverse events with BIC/F/TAF.

1.2 Study Objectives

The specific aims of this study are as follows:

1. To determine the efficacy, safety, and tolerability of Bictegravir/Emtricitabine/Tenofovir Alafenamide (BIC/F/TAF) in HIV+ patients post renal transplant.
2. To assess the pharmacokinetics and drug/drug interactions with immunosuppressive agents (tacrolimus) of BIC/F/TAF in HIV+ patients post renal transplant and preservation of renal function.

1.2.1 Primary Objectives

The primary objectives of this study are as follows:

1. To determine the efficacy of BIC/F/TAF in HIV+ patients post renal transplant.
2. To assess the safety and tolerability of BIC/F/TAF in HIV+ patients post renal transplant.
3. To assess the pharmacokinetics of BIC/F/TAF in HIV+ patients post renal transplant and its interactions with immunosuppressive agents (Tacrolimus).
4. To assess renal biomarkers including urine protein/creatinine ratio; urine albumin/creatinine ratio; eGFR; serum BUN, creatinine and phosphorus; tacrolimus levels; retinol 2 binding protein and B2 microglobulin post renal transplant.

1.2.2 Secondary Objectives

1. To assess the incidence of kidney graft rejection after switching to BIC/F/TAF post renal transplant.
2. To assess the immunologic activity (CD4 count/percentage) of BIC/F/TAF post renal transplant in conjunction with immunosuppressive agents (tacrolimus).
3. To determine patient satisfaction with BIC/F/TAF post renal transplant by utilizing a questionnaire to assess health-related quality of life outcomes.

2. Background

At NewYork-Presbyterian Hospital-Weill Cornell Medicine, we have a robust Renal Transplant Program, including renal transplantation in HIV+ patients. The Renal Transplant Program works in close collaboration with the Transplant/Oncology Infectious Diseases Program, including clinical research trials. There have been 42 renal transplants performed in HIV+ patients at our institution in the past 10 years, including two HIV to HIV renal transplants. Thirty-seven patients (excluding HIV to HIV renal transplants) remain alive and are eligible for study consideration. Only four are receiving TAF-containing regimens; the remaining 33 are on various antiretroviral (ARV) regimens including protease inhibitors, cobicistat and ritonavir (started by and maintained by their community HIV primary care physicians), which increase drug-drug interactions with tacrolimus and jeopardize the kidney transplant, as well as increasing pill burden. Therefore, a new single tablet ARV with less

drug-drug interactions is important to this unique population. Data from 4 clinical trials (1-5) show that the single tablet regimen containing BIC/F/TAF (Bictegravir/Emtricitabine/Tenofovir Alafenamide) is safe and efficacious and non-inferior to other standard ARV regimens. No patients had to discontinue the drug due to renal events and no patients developed treatment-emergent resistance. BIC had no impact on severe renal impairment (eGFR_{CRG} 15-29 mL/min), no effect on actual GFR (iohexol clearance) and minimal effect on estimated GFR. There were no discontinuations due to adverse renal events and no proximal renal tubulopathy. TAF is a novel tenofovir prodrug (6,7) with improved renal and bone safety compared to Tenofovir. As reported in JAIDS 2016 (5), switching HIV-positive patients with mild to moderate renal impairment from a prior TDF-based regimen to Elvitegravir/Cobicistat/Emtricitabine/TAF (E/C/F/TAF) resulted in significant decreases in proteinuria, albuminuria and tubular proteinuria without dose adjustment.

Kidney transplantation is successful in HIV+ patients although rejection rates are higher than in non-HIV+ transplant patients (8). The greatest clinical challenge is to achieve therapeutic and nontoxic levels of the immunosuppressive drugs, especially Tacrolimus, in this population, due to the complicated pharmacokinetic interactions of these agents with antiretroviral agents (ARV), especially protease inhibitors, cobicistat, and ritonavir (8). Non-therapeutic exposure to tacrolimus contributes to higher rate of rejection, so it is important to study ARV agents with less drug-drug interactions that are safe in this special population. We are currently completing a manuscript addressing this issue at our institution and the kidney transplant team has presented preliminary data in a poster at the American Transplant Congress in 2018 (Al Jurdi, Clinical Outcomes of HIV-Infected Kidney Transplant Recipients With An Early Corticosteroid Withdrawal Protocol). It is important to closely follow the CD4 lymphocyte counts and percentages in this unique population and the effect on HIV infection and immunosuppression. Preferred ARV regimens in HIV+ patients post renal transplant include integrase inhibitors and TAF, with the goal to avoid protease inhibitors, ritonavir and cobicistat and decrease drug-drug interactions with tacrolimus (8,9).

In treatment naïve adults with HIV-1 infection, switching from DTG, abacavir, and lamivudine to BIC/F/TAF proved to be a safe and efficacious option for the treatment of HIV-1 infection (1). The pharmacokinetics of BIC/F/TAF were assessed in this study, and the mean trough concentrations of BIC were 14 times higher than the protein-adjusted 95% effective concentration against wild type HIV-1 virus.

There is no current data about the pharmacokinetics of BIC/F/TAF in renal transplant recipients or the interactions of BIC/F/TAF with tacrolimus. Previous work has demonstrated sustained, zero-order, linear, release pharmacokinetic characteristics of TAF (10,11). TAF is metabolized via CES1 in hepatocytes, cathepsin A in PBMCs, and minimally with CYP3A. Tenofovir plasma levels significantly increase when administered to subjects with moderate to severe renal impairment, such that the dosing interval is adjusted in patients with baseline creatinine clearance below 50 mL/min based on modeling of single-dose pharmacokinetic data in non-HIV and non-HBV infected subjects with varying degrees of renal impairment (12).

TAF is hydrolyzed within cells to form tenofovir (major metabolite), which is phosphorylated to the active metabolite, tenofovir diphosphate. *In vitro* studies have shown that TAF is metabolized to tenofovir by CES1 in hepatocytes, and by cathepsin A in PBMCs and macrophages. Whether tenofovir can accumulate and lead to nephrotoxicity in conjunction with tacrolimus after tenofovir

alafenamide administration is not known. Moreover, the long-term renal safety of tenofovir alafenamide in HIV+ renal transplant recipients receiving tacrolimus is not known.

Dried blood spots have been used to determine markers of recent dosing and measures of anti-retroviral adherence (13,14). Comparison of tenofovir and FTC in dried blood spot versus plasma indicated that dried blood spot can be used as a plasma alternative for pharmacokinetic analyses in vivo (15). Measurement of intracellular TAF levels has not been done in the HIV+ renal transplant population. We will therefore incorporate the dried blood spot method and PBMC method to determine intracellular TAF levels and monitor adherence in the renal transplant population.

We therefore will determine concentrations of BIC, FTC, and TAF in serial samples of plasma and peripheral blood mononuclear cells over the course of 48 weeks in HIV+ renal transplant recipients (Section 6.1).

Preservation of renal function and graft survival is of primary importance in this HIV-infected renal transplant population, challenged by drug-drug interactions between ARV regimens and anti-rejection medications. In the 112 study (5), switching to E/C/F/TAF had no change in estimated or actual GFR and proteinuria, proximal renal tubular function, and BMD significantly improved over 48 weeks. In patients with eGFR <50 mL/min, adverse events were similar in grade and frequency to patients with GFR>50 mL/min. BIC/F/TAF has demonstrated high rates of virologic suppression and no treatment-emergent resistance through 48 weeks in phase 3 clinical trials among treatment naïve adults and among virologically suppressed adult patients who switched ARV regimens. Therefore, BIC/F/TAF promises to be an important ARV regimen to be studied in HIV+ post renal transplant patients, including drug-drug interactions with anti-rejection agents, especially tacrolimus. Pharmacokinetic studies, and drug-drug interactions are important to study in this unique population, as well as the efficacy, safety and tolerability of BIC/F/TAF.

In this single arm, open-label, switch study, we propose to switch virally suppressed HIV+ adults post-renal transplant to BIC/F/TAF and follow the subjects for 48 weeks to evaluate the efficacy, safety and tolerability of BIC/F/TAF, plus a 6 month follow-up. Health related quality of life outcomes are important in the evaluation of ARV treatment strategies, especially in the HIV+ renal transplant population. BIC/F/TAF and DTG-based regimens have been compared in treatment-naïve and HIV-1 suppressed adults, showing non-inferior efficacy and less drug-related adverse events in BIC/F/TAF arms compared to DTG-based regimens. To better understand the patients' experience with BIC/F/TAF post renal transplant, we will be using a specific quality of life questionnaire (Attachment 1). We hypothesize that BIC/F/TAF will be an important addition to the management of HIV+ post renal transplant patients, especially since it is a one pill daily dosing regimen, thereby decreasing the pill burden in this unique population.

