3.1 Overall Design

We hypothesize that BIC/F/TAF will be efficacious and safe in the management of HIV+ post renal transplant patients, and will have few adverse reactions and drug-drug interactions with tacrolimus in this population.

Eighteen subjects will be enrolled in this Phase IV, single arm, open-label, single-site, switch study. In this study, virally suppressed HIV+ adults will be switched post-renal transplant from their current anti-retroviral regimen to BIC/F/TAF and will be followed for 48 weeks with a 6 month follow-up (Section 6.1). Informed consent will be obtained before starting the study (Section 6.1).

Patients will have bloodwork completed throughout the study, as shown in the Schedule of Assessments (Section 6.1).

A health-related quality of life questionnaire (Appendix) will be administered to each patient to assess satisfaction with a one pill regimen as well as adverse events (Section 6.1).

Pharmacokinetic (PK) studies will be assessed at Week 12 when the renal function is stable (decided by PI). Intracellular TAF levels by dried blood spot will be collected during the Week 12 visit as well as Week 24, Week 36, Week 48, Month 6 Follow-up. Intracellular TAF levels by PBMC will be collected once during the Week 12 visit. An intensive pharmacokinetic day will take place at the Week 12 visit. This bloodwork is outlined in Section 6.1. Bloodwork for the intracellular TAF level testing and pharmacokinetic testing will be stored and sent to [name] at the University of Colorado's Antiviral Laboratory. (14-16)

Note: Patients switched post-renal transplant from their current anti-retroviral regimen to BIC/F/TAF prior to identification for this study may also be enrolled. This group will be referred to as "Group 2". Pharmacokinetic testing for Group 2 subjects will be completed once each Group 2 subject's tacrolimus levels are stable as per the Principal Investigator for 2-4 weeks. All standard of care lab values and concomitant medications will be collected from Group 2 subjects for 60 days prior to and after the Biktarvy switch date and for the duration of Biktarvy therapy. Any adverse events related to Biktarvy prior to enrollment will be recorded.

Sample Collection

Samples include plasma and peripheral blood mononuclear cells (PBMC). Blood is collected in EDTA tubes for plasma separation. CPT vacutainers are used to isolate PBMC, which are counted with an

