Appendix. HIV Treatment Satisfaction Questionnaire

HIV TREATMENT SATISFACTION QUESTIONNAIRE

SUBJECT IDENTIFIER _____

DATE _____

The following questions are concerned with your medical treatment for HIV and your experience over the past few weeks. Please answer each question by circling a number on each of the scales.

1. How satisfied are you with your current treatment?

very satisfied 6 5 4 3 2 1 0 very dissatisfied

2. How well controlled do you feel your HIV has been recently?

very well controlled 6 5 4 3 2 1 0 very poorly controlled

3. How satisfied are you with any side effects of your present treatment?

very satisfied 6 5 4 3 2 1 0 very dissatisfied

4. How satisfied are you with the demands made by your current treatment?

very satisfied 6 5 4 3 2 1 0 very dissatisfied

5. How convenient have you been finding your treatment to be recently?

very convenient 6 5 4 3 2 1 0 very inconvenient

6. How flexible have you been finding your treatment to be recently?

very flexible 6 5 4 3 2 1 0 very inflexible

7. How satisfied are you with the extent to which the treatment fits in with your lifestyle?

very satisfied 6 5 4 3 2 1 0 very dissatisfied

8. Would you recommend your present treatment to someone else with HIV?

yes, I would recommend 6 5 4 3 2 1 0 no, I would definitely not recommend

9. How satisfied would you be to continue with your present form of treatment?

very satisfied 6 5 4 3 2 1 0 very dissatisfied

Please make sure that you have circled one number on each of the scales.

Thank you for taking the time to complete this questionnaire.

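### The questionnaire is described as measuring health-related quality of life, but the form supplied measures HIV treatment satisfaction and bears on reduced pill burden only indirectly

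*Combined protocol and SAP*

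**What the plan says.** Secondary objective 3 (synopsis and Section 1.2.2) is "To determine patient satisfaction with BIC/F/TAF post renal transplant by utilizing a questionnaire to assess health-related quality of life outcomes". The synopsis sets it at weeks 24 and 48. In Section 2 (Background) the protocol says "we will be using a specific quality of life questionnaire (Attachment 1"). Sections 3.1 and 6.1 both describe the Appendix form as a health-related quality-of-life questionnaire, given "to assess satisfaction with a one pill regimen as well as adverse events".

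Secondary endpoint 3, in the synopsis, is "Patient satisfaction with reduced pill burden and adverse events with BIC/F/TAF". It does not name quality of life.

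The form in the Appendix is titled "HIV Treatment Satisfaction Questionnaire" and opens: "The following questions are concerned with your medical treatment for HIV and your experience over the past few weeks". It has nine items, each on a 0 to 6 scale, and gives no scoring rule. The Schedule of Assessments (Section 6.1) marks booklet administration on Day 1. It marks completion at Weeks 4, 12, 24, 36 and 48, at follow-up Months 3 and 6, and at unscheduled visits. The statistical text (Sections 3.1 and 10.1) provides for descriptive statistics on outcomes in general and says nothing specific to the questionnaire.

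**The concern.** Treatment satisfaction and health-related quality of life are different constructs. A patient can be content with a tablet while in poor health, or the reverse. If the objective is reported as worded, a satisfaction score could be presented as a quality-of-life finding with no quality-of-life data behind it.

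A second inference is also exposed. The endpoint speaks of a reduced pill burden, which implies a comparison with the previous regimen. That needs to be known for each subject, both in pills taken and in satisfaction before the switch, if satisfaction is to be attributed to taking fewer pills.

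**Working it through.** The plan gives no figure for this endpoint, so the check compares content and schedule.

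**Step 1. The nine Appendix items against the three things the protocol says the form covers.**

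| Item | Subject of the item | Health status or functioning | Names pills | Side effects |
|---|---|---|---|---|
| 1 | Overall satisfaction | no | no | no |
| 2 | Perceived HIV control | no | no | no |
| 3 | Side effects | no | no | yes, as satisfaction |
| 4 | Demands of treatment | no | no | no |
| 5 | Convenience | no | no | no |
| 6 | Flexibility | no | no | no |
| 7 | Fit with lifestyle | no | no | no |
| 8 | Would recommend | no | no | no |
| 9 | Content to continue | no | no | no |
| Total | | 0 of 9 | 0 of 9 | 1 of 9 |

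Item 7 comes nearest to quality of life, but it rates satisfaction with the treatment. Item 3 reads "How satisfied are you with any side effects of your present treatment": it records an attitude, not an event. Items 4 to 7 bear on regimen burden. Item 4, for instance, asks "How satisfied are you with the demands made by your current treatment". None of them separates the number of tablets from other features of the regimen.

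**Step 2. Is there another instrument?** The Schedule lists no other patient-reported measure. The Background cites Attachment 1 while Sections 3.1 and 6.1 cite the Appendix. Only the Appendix form is in the documents, and I take the two to be the same.

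**Step 3. Is there a pre-switch score?** The first marked completion is Week 4. The form asks about current treatment over recent weeks, so for a subject who switched on Day 1 that answer describes BIC/F/TAF. Scheduled completions on the prior regimen: 0. Group 2 subjects (Section 3.1) switched before being identified for the study and cannot give one.

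**Step 4. Is the change in pill number known?** Section 2 says that 33 of the 37 candidates are on various regimens and that these add to pill burden; the other 4 are on TAF-containing regimens. It gives no pill counts. The protocol specifies no field for the daily antiretroviral pill number before the switch. For Group 2, concomitant medications are collected from 60 days before the switch (Section 3.1 and the Schedule footnote on safety labs), so the number may be recoverable there. No equivalent collection is stated for the other subjects.

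**The case against.** The best defence is that objective 3 and endpoint 3 both have patient satisfaction as their subject, and the form measures exactly that. No listed endpoint names quality of life, so the fault may be no more than a loose descriptive phrase. This largely stands. A reader might infer that the objective and endpoint are answered by a measure of something else altogether, and the documents do not support that. What remains is that the quality-of-life label appears in the objective itself and in Sections 2, 3.1 and 6.1, and nothing measures it.

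A reader might also infer that the form has no adverse-event content. That is wrong: item 3 addresses satisfaction with side effects, which is the adverse-event half of endpoint 3. Occurrence goes on the adverse event log (Section 11.2). Only the reading that the form itself establishes whether events occurred fails.

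On pill burden, the defence is that every treated subject takes one tablet, that the Background gives a reason to expect a reduction, and that items 4 to 7 are relevant. All true, but an expected reduction in the cohort is not a known reduction in each subject.

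Finally, Section 8 says that REDCap will capture all treatment data, and the case report form is not in the documents. It would therefore be too strong to say that prior pill number is not collected; it is not specified. Likewise, Day 1 booklet administration might in practice include completing the form, but the Schedule has a separate completion row, and that row has no mark on Day 1.

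**Conclusion.** The point holds in this form: 0 of 9 items measure health status or functioning, 0 of 9 name pills, and 1 of 9 concerns side effects, as satisfaction only. The trial can report HIV treatment satisfaction. It cannot report a quality-of-life outcome, and as scheduled it cannot tie satisfaction to fewer pills.

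It is tempting to estimate the share of subjects whose pill number did not fall. The documents give no basis for any such figure, and I offer none.

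The conclusion assumes that the Appendix form is the only questionnaire and that the Schedule's completion row means what it says. It concerns one secondary objective and endpoint in a feasibility-sized pilot with descriptive reporting. Neither the primary endpoint nor the sample size is affected.

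**What to change.** 1. Reword secondary objective 3 (synopsis and Section 1.2.2) and the matching text in Sections 2, 3.1 and 6.1 as HIV treatment satisfaction. Drop the quality-of-life claim and confirm that Attachment 1 is the Appendix form.
2. State that adverse-event occurrence comes from the adverse event log and that item 3 gives satisfaction with side effects.
3. Reword secondary endpoint 3 as treatment satisfaction at Weeks 24 and 48, with items 4 to 7 reported as treatment demands and convenience.
4. Record the daily number of antiretroviral pills on the pre-switch regimen. Use the phrase reduced pill burden only for subjects whose count fell.
5. Have subjects not yet switched complete the same form on Day 1 before switching. A pill count alone, without this score, cannot show that satisfaction changed with fewer pills. Report Group 2 separately, since its members cannot supply a pre-switch score.

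The trial gives up a quality-of-life claim and adds one data field and one form at an existing visit. No new instrument is needed.
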